1 PROTOCOL SUMMARY

Protocol Title	An exploratory Phase 1 mechanism-of-action study of ZB-06, a vaginal film containing HC4-N, an anti-sperm monoclonal antibody
Protocol Number	ZB-06-01
Short Title	In vivo anti-sperm activity of ZB-06 film
Sample Size	Screen ~ 60 couples to complete 15 evaluable couples
Population	Healthy women $18 - 50$ years of age, who have normal menstrual cycles and are not at risk of pregnancy due to prior surgical sterilization, and their male partners, with whom they are in a monogamous sexual relationship
Centers	One: Eastern Virginia Medical School
Study rationale	This study is intended to make a preliminary assessment of the potential contraceptive effectiveness and safety of ZB-06 by observing its ability to reduce motile sperm access to the endocervix.
Study Design	This is an exploratory Phase 1, single center, open-label, crossover, mechanism of action study using a surrogate marker for contraceptive efficacy (the Standardized Postcoital Test, PCT) to assess the contraceptive potential of the ZB-06 film. The study will enroll up to 35 couples to reach a total of 15 fully evaluable women who have completed the baseline and the active-product post-coital visits. The expected duration of study participation for each
	participant will be approximately three months, including the screening period.
Schedule of Procedures/Evaluations	Visit 1: Screening Visit 2: Enrollment Visit 3: Cervical mucus check at midcycle Visit 4; Baseline (no product) postcoital visit Visit 5: 24-hour follow-up Visit 6: Cervical mucus check at midcycle Visit 7: Postcoital visit after intercourse using ZB-06 film Visit 8: 24-hour follow-up Visit 9: Cervical mucus check at midcycle Visit 10: No-product postcoital visit 1 month after ZB-06 film use

Study Duration	Estimated total study duration, 18 months; individual participation, three months				
Test product, dose, and mode of administration	ZB-06 film: The ZB-06 film contains 20 mg of the HC4-N sperm-agglutinating antibody which will be digitally inserted into the vagina by the participant 30 min before intercourse timed to midcycle, after documentation of sperm-receptive endocervical mucus in the preceding mucus check visit.				
Reference therapy, dose, and mode of administration	Baseline PCT cycle, conducted without use of ZB-06 film				
Primary Objective	To assess the potential contraceptive activity of the ZB-06 film using a surrogate assessment for contraceptive efficacy: the degree to which progressively motile sperm can be excluded from the endocervical mucus after intercourse preceded by a single administration of the ZB-06 film, compared to the same evaluation performed after intercourse without film.				
Secondary Objectives	 To assess the safety of a single dose of ZB-06 film preceding a single act of vaginal intercourse 				
Exploratory Objectives	 To determine antisperm antibody concentrations and agglutination potency in vaginal fluids, endocervical mucus, and serum at baseline, and at 2-3 and 24 hours after intercourse with and without product use, and after intercourse without product, 1 month after product use To assess the effect of the film on cervicovaginal immune mediators 				
Primary Endpoint	Number of progressively motile sperm in aspirated endocervical mucus at Visit 7, 2-3 hours after sexual intercourse using ZB-06 film.				
Secondary Endpoints	Incidence of Grade 2 or greater adverse events in the participant and/or her male partner in the interval between Visit 4 (the baseline intercourse without product) and Visit 6, in comparison to the incidence of Grade 2 or greater adverse events in the interval between Visit 7 (intercourse with product) and Visit 9.				

	r	
Exploratory Endpoints	1.	Concentrations of anti-sperm-antibody in vaginal fluid measured by ELISA at baseline, at 2-3 hours, and at 24 hours after intercourse with and without product use, and at 1 month after product use
	2.	Sperm agglutination titer in vaginal fluid measured by endpoint dilution at baseline, and at 2-3 hours and at 24 hours after intercourse with and without product use, and at 1 month after product use
	3.	Concentrations of anti-sperm-antibody in endocervical mucus measured by ELISA at baseline, and at 2-3 hours and at 24 hours after intercourse with and without product use, and at 1 month after product use
	4.	Sperm agglutination titer in endocervical mucus by endpoint dilution measured at baseline, and at 2-3 hours and at 24 hours after intercourse with and without product use, and at 1 month after product use
	5.	Concentrations of anti-sperm antibodies in serum measured by ELISA at baseline, at 24 hours, and at 1 month after exposure to ZB-06 film
	6.	Sperm agglutination titer in serum by endpoint dilution measured at baseline, and 24 hours and 1 month after exposure to ZB-06 film
	7.	Concentrations of immune mediators in cervicovaginal lavage, measured via multiplex assays before and 24 hours after intercourse with vs. without study product.
	8.	Vaginal pH at baseline and 24 hours after intercourse with vs. without study product.
	9.	Nugent Score at Visit 6 baseline and 24 hours after intercourse with study product.

2 INTRODUCTION

2.1 Background

2.1.1 Product description

ZB-06 is an intravaginal film containing 20 mg of the HC4-N drug substance, an IgG1 monoclonal antibody that binds to CD52g, a glycoform expressed on the surface of human sperm. Note that HC4-N targets a unique glycan (CD52g) attached to a 12 amino acid peptide sequence designated CD52 (Diekman *et al.*, 2000). The CD52 peptide is abundant on the surface of human lymphocytes and other immune cells, but the molecule on immunocytes lacks the male-tract specific glycan CD52g. HC4-N does not bind to the CD52 peptide, and thus does not bind immune cells, but binds only to the male-tract specific glycan CD52g expressed on sperm. When HC4-N binds to sperm, it cross-links them causing them to agglutinate. The additional constituents of the film are a film-forming polymer (polyvinyl alcohol, PVA), maltitol, histidine, and polysorbate 20. The film is approximately 2" x 2".

2.1.2 Study rational

The primary objective of the study is to determine whether the ZB-06 film's novel mechanism of action, antibody mediated sperm agglutination, shows promise in a surrogate-efficacy proof-of-concept assessment.

Two lines of *in vivo* evidence suggest that human anti-sperm antibodies may be effective. First, an agglutinating anti-sperm antibody was shown to be effective as a contraceptive in rabbits (Castle *et al.*, 1997). And second, anti-sperm antibodies are observed in women suffering from immune infertility (Ustay, 1967; Bronson 1999). Indeed, the HC4-N antibody was cloned from circulating B-cells of an infertile woman with high-titer anti-sperm antibodies in her blood and genital tract, and without other explanation for her infertility (Isojima S, 1989). However, while *in vitro* and *in vivo* data suggest that an anti-sperm antibody might be efficacious, a demonstration of sperm inhibition in women would be an essential demonstration to justify the continued development of anti-sperm antibodies as nonhormonal contraceptives. This Phase 1 exploratory proof-of-concept study of ZB-06 will provide the evidence on mechanism of action of this HCA, HC4-N.

The assessment that will be used to assess the mechanism of action and potential efficacy of the ZB-06 film is termed the Standardized Postcoital Test (PCT). This protocol, developed by CONRAD and Eastern Virginia Medical School in 1995, has become recognized as the appropriate early assessment of intravaginally-active contraceptive methods, including vaginal spermicides and cervical barrier devices (Archer *et al.*, 1995; Mauck *et al.*, 1997; Mauck *et al.*, 2004; Burke *et al.*, 2010; Mauck *et al.*, 2017). We propose using the PCT to evaluate the highly novel mechanism of the ZB-06 film, namely sperm agglutination via antibody-mediated crosslinking. The PCT is an appropriate test at this exploratory stage of product development because a) multiple vaginally-active contraceptive sthat have been judged promising during PCT evaluations have gone on to show contraceptive effectiveness in human contraceptive

trials (Shihata and Trussell, 1991; Mauck *et al.*, 1996; Mauck *et al.*, 1999; Barnhart *et al.*, 2007; Burke *et al.*, 2010; Schwartz *et al.*, 2015; Barnhart *et al.*, 2016), and b) the PCT allows testing in women without putting them at risk of pregnancy because it is conducted in women who have been surgically sterilized. The latter consideration is particularly important because since the HC4-N target (the CD52g antigen) is not present on the sperm of other species (other than chimpanzee), preceding animal contraceptive testing of HC4-N has not been possible. Moreover, the novelty of this approach (there are no other contraceptives based on spermagglutinating antibodies) makes it difficult to determine its likely contraceptive efficacy. Thus, a mechanism-of-action study using the PCT protocol in sterilized women, is an appropriate early step in the assessment of the viability of this novel concept.

Conducting this exploratory study in sterilized women is also appropriate in light of the potential risk of sperm-antibody immune complexes inducing an active anti-sperm immune response that might prolong the contraceptive effect beyond the duration of the HC4-N antibody product in the female reproductive tract. We judge this to be an unlikely outcome but have nevertheless designed the study to investigate this possibility by including an additional study PCT cycle one month after the PCT cycle using the ZB-06 film. We will thus be able to make a preliminary assessment of a potential actively induced anti-sperm antibody response to the use of the ZB-06 film during semen exposure after unprotected intercourse.

Finally, this study will make preliminary assessments of safety and pharmacokinetics of the ZB-06 film.

2.1.3 Dose rationale

The amount of HC4-N mAb, 20 mg per ZB-06 DP film, matches the total mAb concentration for the similar MB66 film studied previously, containing anti-viral antibodies intended for prevention of HIV and HSV. Three lines of evidence suggest that the dose of HN4-N in ZB-06, inserted intravaginally 30 minutes to 4 hours post ZB-06 insertion, will be sufficient to prevent the large majority of sperm from reaching the upper region of the cervix post coitus:

- Concentration of HC4-N needed for sperm agglutination *in vitro*: The concentration of HC4-N needed to agglutinate sperm within ~100 seconds is 40 μg/mL. The resting volume of intravaginal fluid has been estimated to be approximately 1 mL (Owen and Katz, 1999), with coital increases due to sexual excitement and semen deposition, typically raising the total volume to between 3 and 10 mL. A 20 mg dose of HC4-N would be expected to result in an antibody concentration of ~ 2,000 ug/mL.
- 2. Concentration of HC4-N needed for sperm agglutination in a surrogate sheep study: As a preliminary test of *in vivo* vaginal sperm agglutination in an animal model with similar vaginal dimensions to humans, 1 mL of HC4-N (333 ug/mL and 33 ug/mL; n = 3 for each group) in PBS, or PBS alone was instilled into the vaginas of sheep, with the investigators blinded as to the presence or absence and concentration of the antibody. Coital stirring was mimicked by stirring with a vaginal dilator for 10 seconds. Five minutes after dosing, 1 mL of fresh, liquified, pooled human semen was instilled, and

an additional five thrusts with the vaginal dilator were performed. Two minutes after instillation of semen, vaginal fluid was aspirated and immediately assessed for the number of progressively motile sperm. Expressed as a percentage reduction in progressively motile sperm from that observed in the PBS control, the reduction was 100% after instillation of 333 ug/mL (333 ug total dose), and 44% after instillation of 33 ug/mL (33 ug total dose).

3. Monoclonal antibody concentration *in vivo* from the MB66 clinical study: From the pharmacokinetic (PK) data from the MB66-01 clinical trial (Politch et al., submitted), the concentration of VRC01 at 1 and 4 hours after application of MB66 is ~500 microgram/mL at the cervical os. As the amount of VRC01 is 10 mg/ MB66 film, and the amount of HC4-N in a ZB-06 film is 20 mg, the anticipated concentration of HC4-N mAb is twice this, thus ~1,000 ug/mL.

Dose selection summary: As the concentration of HC4-N needed for complete sperm agglutination is ~40 microgram/mL *in vitro* and 33-333 microgram/mL in the sheep model, we anticipate that the concentration predicted by the VRC01 PK data at 1 and 4 hr post application (~1,000 ug/mL at the cervical os) will be sufficient to agglutinate all or nearly all sperm in the ejaculate. The dose of 20 mg of HC4-N per film is near the maximal dose that can be formulated into a film of this size and composition. We have chosen to use this near maximum Mab dose in order to improve the probability of robust protection. We have a high expectation of safety for these antibodies, which are fully human amino acid sequences with glycosylation patterns very similar to those of human antibodies. We believe such antibodies justify a strategy of choosing a dose near the practical limit in order to improve potency and duration of action.

2.1.4 Nonclinical Studies:

A brief summary of the nonclinical safety studies performed with ZB-06 is provided below. Additional details can be found in the Investigator's Brochure for ZB-06.

2.1.4.1 Tissue Cross Reactivity

A tissue cross reactivity study was performed to determine the potential cross reactivity of HC4-N with cryosections from a full panel of normal human, non-human primate (cynomolgus monkey), and rat (Sprague-Dawley) tissues. Epithelial cells in the human epididymis were selected as an ancillary control tissue due to the reported expression of CD52g in this tissue element (Johnston, *et al.*, 2020; Norton, *et al.*, 2002). In order to detect binding, HC4-N was applied to cryosections of tissues at two concentrations (10 and $2 \mu g/mL$).

HC4-N stained the membrane and cytoplasm of epithelial cells in human epididymis consistent with the reported expression of CD52g in this cell type. In addition, membrane and cytoplasmic staining was observed with HC4-N in mesothelial cells in several tissues and ovarian surface epithelial cells in all three species, as well as in mononuclear cells in the rat spleen, although no literature was located describing CD52g expression by any of these cell types. HC4-N

produced cytoplasmic reactivity in retinal cells in all species, mononuclear cells in humans, lymphocytes in humans, and epithelial cells in a few tissues in all species. The reactivity in these cell types was restricted to the cytoplasmic compartment, and monoclonal antibody binding to cytoplasmic sites in tissue cross-reactivity studies generally is considered of little to no toxicologic significance due to the limited ability of antibody drugs to access the cytoplasmic compartment in vivo (Hall, *et al.*, 2008; Leach, *et al.*, 2010).

2.1.4.2 Rat toxicology test

An *in vivo* toxicology study was performed to evaluate the potential effects, identify target organs of toxicity, and to estimate the no observed adverse effect level (NOAEL) and the maximum tolerated dose (MTD) of ZB-06 after 9 consecutive intravaginal administrations to adult, female Sprague Dawley rats followed by 14 days of recovery.

All animals survived to the end of the study, and there were no test-article related body weight changes, clinical observations, clinical chemistry, urinalysis, gross necropsy, or histopathology findings that were considered to be toxicologically significant. Minimal, reversible changes in hematology were observed in the high-dose group compared with the control group, however there were no correlating macroscopic and microscopic findings or irritation associated with ZB-06 treatment, therefore these changes were not considered to be adverse.

Based on the absence of any irritation or any toxicologically significant adverse effects in any of the parameters evaluated following daily intravaginal administration of ZB-06 for 9 days to adult female rats, the NOAEL for ZB-06 was considered to be 5 mg/day. A maximum tolerated dose could not be determined in the study.

2.1.4.3 Rabbit vaginal irritation test

A rabbit vaginal irritation study was performed to evaluate the potential for vaginal irritation following intravaginal administration of ZB-06. The study evaluated once daily intravaginal administration of suspensions of ZB-06 at 1, 4, and 16 mg/mL for 10 consecutive days to New Zealand White Rabbits. Repeat administration of ZB-06 did not result in any meaningful effects on survival, detailed clinical observations, body weight/body weight change, hematology, coagulation, clinical chemistry, macroscopic, or organ weight evaluations. Test article-related microscopic findings were present in the vagina at \geq 4 mg/mL but were not considered adverse due to their lack of severity.

Based on the absence of any adverse effects following once daily intravaginal administration of suspensions of ZB-06 to New Zealand White Rabbits at 1, 4, and 16 mg/mL for 10 consecutive days, the NOAEL for ZB-06 was considered to be >16 mg.

2.1.5 Clinical studies

There have been no human studies of the HC4-N drug substance or the ZB-06 film drug product.

2.1.6 Risks and benefits

This is the first study of ZB-06 in humans, and therefore its risks are not known. The animal studies done to date do not raise significant concerns. Prior clinical experience with similar PVA-based vaginal films such as a marketed nonoxynol-9 based contraceptive film (Vaginal Contraceptive Film, Apothecus Pharmaceutical Corporation), have side effects including vaginal irritation/inflammation, vaginal burning, vaginal discharge, and penile irritation for male sexual partners. Rare but serious side effects may include severe allergic reactions with rash, hives, and itching. There are no expected benefits to study participants, other than the possible satisfaction of having aided in the evaluation of a novel contraceptive method.

3 STUDY OBJECTIVES AND MEASUREMENTS

3.1 Study Objectives

3.1.1 Primary Objective:

To assess the potential contraceptive activity of the ZB-06 film using a surrogate assessment for likely contraceptive efficacy (the degree to which progressively motile sperm can be excluded from the endocervical mucus).

3.1.2 Secondary Objective:

To assess the safety of a single dose of ZB-06 film used with a single act of vaginal intercourse among female participants and their male partners.

3.1.3 Exploratory Objectives:

- To determine antisperm antibody concentrations and agglutination potency in vaginal fluids, endocervical mucus, and serum at baseline, and at 2-3 and 24 hours after intercourse with and without product use, and 1 month after product use
- To assess the effect of the film on cervicovaginal immune mediators

3.2 Study Endpoints

3.2.1 Primary endpoint:

Number of progressively motile sperm in aspirated endocervical mucus 2-3 hours after sexual intercourse using ZB-06.

3.2.2 Secondary endpoint:

Incidence of Grade 2 or greater adverse events in the participant and/or her male partner in the interval between Visit 4 (the baseline intercourse without product) and Visit 6, in comparison to the incidence of Grade 2 or greater adverse events in the interval between Visit 7 (intercourse with product) and Visit 9.

3.2.3 Exploratory endpoints:

- 1. Concentrations of anti-sperm-antibody in *vaginal fluid*, measured by ELISA at baseline, at 2-3 hours, and at 24 hours after intercourse with and without product use, and at 1 month after product use
- 2. Sperm agglutination titer in *vaginal fluid* measured by endpoint dilution at baseline, and at 2-3 hours and at 24 hours after intercourse with and without product use, and at 1 month after product use
- 3. Concentrations of anti-sperm-antibody in *endocervical mucus*, measured by ELISA at baseline, and at 2-3 hours and at 24 hours after intercourse with and without product use, and at 1 month after product use
- 4. Sperm agglutination titer in *endocervical mucus*, by endpoint dilution measured at baseline, and at 2-3 hours and at 24 hours after intercourse with and without product use, and at 1 month after product use
- 5. Concentrations of anti-sperm antibodies in *serum*, measured by ELISA at baseline, at 24 hours, and at 1 month after exposure to ZB-06 film
- 6. Sperm agglutination titer in *serum* by endpoint dilution measured at baseline, and 24 hours and 1 month after exposure to ZB-06 film
- 7. Concentrations of immune mediators in cervicovaginal lavage, measured via multiplex assays before and 24 hours after intercourse with and without study product.
- 8. Vaginal pH at baseline and 24 hours after intercourse with vs. without study product.
- 9. Nugent Score at Visit 6 baseline and 24 hours after intercourse with study product.

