4 INVESTIGATIONAL PLAN

4.1 Study Design

This is a Phase 1, single center, open label, non-randomized, crossover, mechanism of action study, using a surrogate marker for contraceptive efficacy (the Standardized Postcoital Test, PCT) to assess the mechanism of action and contraceptive potential of the ZB-06 film.

The product to be tested is the ZB-06 vaginal film, containing 20 mg of the HC4-N anti-sperm antibody. Participants will be women who are not at risk for pregnancy due to surgical sterilization, and their male sexual partners. The individual evaluating the cervical mucus for midcycle characteristics and presence of sperm will be blinded as to the treatment cycle. Each participant will be seen in approximately ten visits, over a period of 3 - 6 months. Volunteers will be consented at Visit 1 and undergo procedures to confirm they are eligible to continue in the study. Each participant will undergo three PCT cycles. The first PCT cycle will be a baseline cycle, done without the use of any product, in order to demonstrate the participant's ability to undergo normal ovulatory events and to produce receptive, midcycle cervical mucus. The male partner's ability to produce motile sperm capable of penetrating the cervical mucus is also evaluated in this baseline cycle. A product use PCT cycle will be carried out during the subsequent menstrual cycle using the ZB-06 film. An additional PCT cycle without product will be carried out during the subsequent menstrual cycle. Cycles may need to be repeated depending on the characteristics of the cervical mucus and the number of sperm found in the vaginal pool and endocervical specimens (see Appendix B).

The primary endpoint will be an assessment of the potential contraceptive activity of the ZB-06 film using a surrogate assessment for contraceptive efficacy, i.e., observing the degree to which progressively motile sperm can be excluded from the endocervical mucus.

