- The participant will be asked whether she refrained from intercourse and the use of intravaginal products and whether her male partner refrained from ejaculation during the previous 72 hours. If instructions were not followed, she will be reinstructed. If she used a spermicide or spermicidally lubricated condom during the previous 72 hours, the visit will be rescheduled in the next cycle. Otherwise, the visit may continue at the investigator's discretion.
- Urine will be obtained for urinalysis and reflex urine culture at visits 3 and 6.
- A urine pregnancy test will be performed at visit 6
- A blood sample (approximately 3 teaspoons) will be obtained at visits 6 and 9. The participant will undergo a pelvic exam during which a sample of cervical and vaginal secretions will be examined for midcycle characteristics and the presence of sperm. At visits 3 and 6, a colposcopy exam of the cervix and vagina will be done to determine if there are signs of irritation of the external genitalia, cervix, and vagina, as observed with the naked eye will be noted.
- Vaginal pH will be determined at visits 3 and 6. A slide for Nugent score will be obtained at visit 6
- A speculum exam will be performed and vaginal swabs, aspirate, endocervical mucus and a cervicovaginal fluid lavage (CVL) will be obtained.
- If sperm are found in the vagina or cervical mucus, the baseline cycle will be rescheduled for the following month and instructions on the use of condoms and avoidance of ejaculation will be reviewed. Longer abstinence may be recommended

for couples that have reportedly complied with the required 72-hour period. Additional supplies will be provided as needed.

- If the cervical mucus score is <10, the participant may be asked to return in 1 or 2 days if it seems likely that the midcycle point has not yet been reached, or in the next cycle if it seems likely that the midcycle point has already passed.
- If no sperm are detected at this visit, and the cervical mucus score is ≥10, the participant will be instructed to return home and have intercourse without a condom 2 to 3 hours prior to Visits 4, 7 or 10, which will be scheduled for the same or following day, within 27 hours of the mucus check visit.

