6.5.5 Visits 5 and 8 (24 hours post PCT safety checks)

- The participant will be asked if she has any new or worsening medical problems or symptoms or used any medications since the last study visit. In addition, she will be asked if her partner has had any AEs involving the urogenital system or associated with the use of study products (as applicable) and whether he has had any serious AEs.
- A colposcopy assessment will be performed
- Vaginal swabs or aspirate, endocervical mucus and a cervicovaginal fluid lavage (CVL) will be obtained.
- A blood sample (approximately two teaspoons) will be obtained.
- Urine will be obtained for urinalysis and reflex urine culture.
- Vaginal pH and slide for Nugent score will be obtained at visit 8.
- At the end of Visits 5 and 8, the participant will be given additional condoms if needed and instructed to contact the study coordinator on the first day of her next menses at which time instructions regarding sexual activity and checking urinary LH will be given. The participant will be reminded that from the start of her menses until menstrual cycle day 10, she and her partner should use study provided condoms for each act of intercourse. There should be no intercourse or use of intravaginal products (including spermicide) after menstrual cycle day 10.
- The participant will be provided with a new ovulation prediction kit. When she contacts the clinic on the first day of her next menses, she will be instructed to begin daily urine testing starting on day 10 of her cycle. She will be instructed to contact the study coordinator if a urine test result is positive. Her test cycle mucus check visit will be scheduled for the day of the positive test (preferred) or the next day at the latest. However, if she has not had a positive urine test result by day 22, she will be considered anovulatory and will either be discontinued from the study or allowed to try another cycle, depending on ZabBio, Inc. and investigator discretion.

- A wet mount or urine dipstick, or other tests, will be performed if indicated. If the test is positive for candidiasis, BV, or UTI the participant will be treated, preferably with oral medication, and continued in the study. Note that these vaginal infections may be treated with vaginal medication subsequent to 24 hr check visits.
- At visit 8, the participant will fill out an acceptability questionnaire.

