6.6 Visit Windows

- Visit 2 must be within 35 days of Visit 1.
- Visits 3, 6, and 9 (CMC visits) timing is determined according to midcycle timing according to calculations and/or OPK testing results rather than visit windows.
- Visits 4, 7, and 10 (PCT visits) must be between 2 and 3 hours after intercourse, with intercourse timing determined by the findings at the preceding CMC visit.
- Visits 5 and 8 (24 hour assessments after the baseline and product PCT visit) must be within 4 hours either side of that scheduled 24 hour follow up time.

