Appendix A. Schedule of Events

PROCEDURE	Visit 1 Screening	Visit 2 Enrollment	Visit 3 Baseline (No-product) CMC	Visit 4 Baseline (No-product) PCT	Visit 5 24 h safety check	Visit 6 Product CMC	Visit 7 Product PCT	Visit 8 24 h safety check	Visit 9 No-product CMC	Visit 10 No-product PCT and Study Exit
Informed consent	Х									
Confirm eligibility	Х	Х								
Dispense informed consent	v									
for male partner	Λ									
Enroll	~ ~	X								
History	X					N 7		N.		NY.
Adverse Event Collection	X	X	X	X	X	X	X	X	X	X
Log concomitant medications	Х	X	X	X	Х	X	Х	X	X	X
Condom and abstinence	Х	Х	Х	Х	Х	Х	Х	Х	Х	
Condom distribution	x				X			x		
Ovulation predictor kit	24									
distribution		Х			Х			Х		
Film insertion training/review	Х					Х				
Film dispensed						Х				
Urine pregnancy test	Х	Δ	Δ	Δ	Δ	Х	Δ	Δ	Δ	Δ
Urinalysis with reflex urine	v		v		v	v		v		
culture	Λ		Λ		Л	Λ		Λ		
NAATS for CT, GC,	х									
Trichomonas										
HIV blood test	X							37		
CBC, Metabolic Panel	X		V			v		X		
Vaginal pH	Δ	٨	X		٨	X		X A		
Slide for Nugart appring	Δ	Δ	Δ		Δ					
Pap	٨					Λ		Λ		
Serum for HC4-N ELISA					x	x	x	x	x	
Serum for sperm					Λ	Λ	Λ	Λ	Λ	
agglutination					Х	Х	Х	Х	Х	
Vaginal swab or aspirate for			v	V	v	v	v	v	v	V
and sperm agglutination assay			Л	А	Л	л	л	Л	Л	А
Endocervical aspirate for										
Insler score, sperm count and			37	37	37	37	37	37	V	37
motility, HC4-N ELISA,			Х	Х	Х	Х	Х	Х	Х	Х
sperm agglutination assay										
CVL for immune mediators			Х		Х	Х		Х	Х	
Vital signs	Х	Δ	Δ	Δ	Δ	Δ	Δ	Δ	Δ	Δ
Directed Physical exam	Х	Δ	Δ	Δ	Δ	Δ	Δ	Δ	Δ	Δ
Pelvic exam	Х		Х	Х	Х	Х	Х	Х	Х	Х
Colposcopy			Х	Х	Х	Х	Х	Х		
Woman's acceptability								X*		
questionnaire										
Man's acceptability								X**		
questionnane										

X Procedure done

 Δ Procedure done if indicated * Women's questionnaire administered at this visit.

**Men's questionnaire administered by telephone within 72 h of intercourse, and will include questions to elicit AEs.

Vaginal pool - any	- any Endocervix								
sperm present (including fragments) *	Mucus - adequate (thin)	No sperm	Some sperm but <5 progressively motile	≥5 progressively motile	Action at Baseline or Safety Cycle	Action at Test Cycle			
Yes	Yes	~			Similar results in test cycle would make				
Yes	Yes		✓		it appear that the product was successful.	Barrier successful			
No	Yes		✓		If this is safety cycle, may indicate	Continue to next cycle.			
Insufficient material	Yes		✓		induction of anti-sperm antibodies				

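### Exploratory endpoint 8 compares 24-hour vaginal pH with and without the film, but no routine pH reading is scheduled at Visit 5, the only no-product 24-hour visit

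*Combined protocol and SAP*

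**What the plan says.** Endpoint 8 is "Vaginal pH at baseline and 24 hours after intercourse with vs. without study product" (Section 3.2.3). The protocol summary and the list in Section 7.5.3 carry the same definition.

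The no-product arm of that comparison is the first cycle. Section 4.1 states: "The first PCT cycle will be a baseline cycle, done without the use of any product". Section 6.6 identifies the 24-hour visits as "Visits 5 and 8 (24 hour assessments after the baseline and product PCT visit", so Visit 5 belongs to the no-product cycle and Visit 8 to the film cycle.

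The pH readings are placed as follows:

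- Section 6.5.3 (mucus-check visits): "Vaginal pH will be determined at visits 3 and 6".
- Section 6.5.5 (Visits 5 and 8 together): "Vaginal pH and slide for Nugent score will be obtained at visit 8". Visit 5 is not named.
- Section 6.5.5 also has a general provision: "A wet mount or urine dipstick, or other tests, will be performed if indicated".

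The neighbouring endpoint 9 is worded more narrowly: "Nugent Score at Visit 6 baseline and 24 hours after intercourse with study product".

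For continuous exploratory variables, Section 7.5.3 assigns the Wilcoxon signed-rank test to two-time-point comparisons and a mixed linear model to three-time-point comparisons.

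**The concern.** The endpoint asks what the film adds to the pH change seen after intercourse alone. That needs a 24-hour reading after intercourse without the film, and the schedule does not collect one routinely. The Visit 3 reading looks like the baseline for the no-product cycle, yet it has no 24-hour partner.

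This is a first-in-human vaginal product. If the only available change is Visit 6 to Visit 8, a shift caused by intercourse could be attributed to the film. A real film effect could also not be separated from the shift caused by intercourse. A reading missed at Visit 5 cannot be recovered later.

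**Working it through.** The plan gives no sample size, power or variability for pH, so there is no figure to reproduce. The check sets the endpoint against the schedule.

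**Step 1. The four readings the comparison needs**

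| Reading | Visit | Routine pH? | Source |
|---|---|---|---|
| No product, before intercourse | 3 | Yes | 6.5.3 |
| No product, 24 hours after | 5 | No | 6.5.5 names Visit 8 only |
| Film, before intercourse | 6 | Yes | 6.5.3 |
| Film, 24 hours after | 8 | Yes | 6.5.5 |

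Three of four are filled. Routine Visit 5 with Visit 8 pairs: 0 of 15 planned evaluable women.

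**Step 2. Could another reading stand in?**

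- *Third cycle.* It ends at Visit 10, the postcoital and exit visit, and has no 24-hour visit.
- *Appendix A.* In the copy available for this review the vaginal pH row is broken and the Visit 5 cell cannot be placed with certainty. It is not a legible X. At most it carries the mark defined as "Procedure done if indicated".
- *Indicated readings.* These would come from women with a clinical reason for testing, not from the evaluable group as a whole.

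Even setting selection aside, indicated readings would have to be fairly common. The smallest two-sided exact signed-rank p-value with n pairs is 2/2^n:

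- n = 5: 2/32 = 0.0625
- n = 6: 2/64 = 0.031

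So at least 6 of 15 women (6/15 = 40%) would need an indicated pH at Visit 5 before p<0.05 was even possible.

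**Step 3. What the available contrasts estimate**

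Write F for the film effect, I for everything else between the mucus check and the 24-hour visit (intercourse, semen, elapsed time, sampling), and C for any difference between cycles.

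- V8 − V6 = I + F
- V8 − V5 = F + C
- (V8 − V6) − (V5 − V3) = F, if I is the same in both cycles

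Only the first can be computed from routine data, and it does not isolate F.

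**Step 4. Illustration of the confounding**

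Assumptions: F = 0, 15 women, normal within-woman changes, exact signed-rank test of Visit 8 against Visit 6 at two-sided 0.05, 20,000 simulated trials. The documents give no value for I, so a range is shown.

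| Assumed I, in SD of the within-woman change | Trials with p<0.05 |
|---|---|
| 0 | 4.7% |
| 0.25 | 13.9% |
| 0.5 | 42.3% |
| 1.0 | 93.9% |

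If Visit 5 is added, 15 pairs give about 80% power for a Visit 8 versus Visit 5 difference of 0.8 SD of the paired difference.

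**Step 5. Comparison with the neighbouring endpoints**

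Endpoint 7 (immune mediators, with and without product) has lavage at Visits 3, 5, 6 and 8, which is the full set. Endpoint 9 is worded for the product cycle and sampled at Visits 6 and 8, which matches. Endpoint 8 is worded like endpoint 7 but, at the 24-hour visits, sampled like endpoint 9.

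**The case against.** The strongest counter-argument is about weight. Endpoint 8 is one of nine exploratory endpoints in an open-label study of 15 women. Neither exploratory objective in Section 3.1.3 mentions pH. Sections 4.1 and 6.2 use cytokines and chemokines as the subclinical safety measure, and the lavage for these is collected at both Visits 5 and 8. The main with-versus-without mucosal comparison is therefore intact. This stands, and it limits the importance of the point.

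Second, the sponsor may have meant a product-cycle pH endpoint and simply worded it too broadly, in which case no sampling needs to change. That is possible, and rewording is an acceptable remedy. The wording and the schedule still disagree until one of them is altered.

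Third, pH at Visits 3, 6 and 8 makes three time points, for which Section 7.5.3 plans a mixed model. That is an analysis of the data collected, but no model over those visits supplies the missing 24-hour no-product value.

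Fourth, the simulation rests on assumed effects and on continuous differences without ties, whereas coarse pH readings would produce ties. The plan also does not say that a Visit 6 to Visit 8 change would be read as a film effect. The percentages are therefore an illustration only; the finding rests on the count of 0 in 15.

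The damaged Appendix A row does not change the result, because the intact visit text shows the gap without it.

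**Conclusion.** The concern holds. Followed as written, the schedule cannot deliver the comparison that endpoint 8 defines: three of its four readings are routine, and the no-product 24-hour reading is routine for none of the 15 planned evaluable women. This is an inconsistency between an endpoint and its sampling schedule, and it should be corrected.

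The conclusion relies on the visit text of Sections 6.5.3, 6.5.5 and 6.6 and on the Visit 5 cell of the Appendix A pH row being no more than an if-indicated mark. Anyone with a clean copy of the table should confirm that cell; an X there would contradict Section 6.5.5, and the two would need to be reconciled. The effect is confined to this one exploratory endpoint.

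**What to change.** Either of two changes resolves it.

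1. **Collect the reading.** Amend Section 6.5.5 so that vaginal pH is taken at Visits 5 and 8, with the Nugent slide remaining at Visit 8, and mark Visit 5 as routine in the Appendix A pH row. Then name the contrast in Section 7.5.3. One option is Visit 8 against Visit 5 within woman by the planned signed-rank test, which assumes no difference between cycles. The other is the baseline-corrected (V8 − V6) − (V5 − V3), which assumes only that the change over time without the film would be the same in both cycles. State the assumption, because cycle order is fixed. Cost: one pH reading per woman at a visit that already has a pelvic examination and swab or aspirate collection, one line of text and one table cell.

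2. **Narrow the endpoint.** Restate endpoint 8 as the Visit 6 to Visit 8 change in the product cycle, in the manner of endpoint 9, and say that it cannot separate the film from intercourse. Cost: one line, repeated in the protocol summary and Sections 3.2.3 and 7.5.3.

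The first keeps the question the endpoint asks; the second gives it up openly.
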